## 10.4 Active Follow-up Period

### Days 4-14 – Surgical resection or biopsy

- Tumor tissue collection (applies to patients who consent to either arm of the study) – this tissue will be taken intraoperatively for pharmacokinetic LC-MS analysis to assess for the presence of evolocumab.
  - Sample will only be taken for analysis if greater than 20 mg of resected or biopsied tissue available (excess available beyond that required for histological analysis)
  - Sample to be aliquoted into 25 mg sections for resections and 10-20 mg (1-2 cores) for biopsies

Treatment arm only:

- Pharmacokinetic blood draw (5 mL, drawn at time of surgery or biopsy, i.e., PK draw may occur either immediately before or during surgery or biopsy)Error! Bookmark not defined.
- Adverse events monitoring

About 2 weeks following surgery or biopsy (treatment arm only)

- Physical and neurological exam
- Laboratory evaluations (obtained as part of standard post-operative labs)
  - CBC with differential
  - CMP
- Adverse events monitoring

## **10.5 End of Treatment**

Once the baseline PK blood draw is collected (both arms) and the evolocumab injection (treatment arm only) is completed, the treatment phase of the study is over and the active follow-up period begins. During the active follow-up period (see Section 10.4), patients undergo their standard of care surgical resection or biopsy with tissue collection, if available. Patients in the treatment arm return for post-surgical wound care about 14 days post-surgical procedure **as needed per standard neurosurgical practice**.

## **10.6 Follow-up Period**

Once active follow-up is complete, patients are followed per standard of care. The study team will review medical records of patients enrolled in the treatment arm to collect information for ongoing serious adverse events and new onset serious adverse events for up to 30 days following Evolocumab injection. If patients subsequently undergo additional biopsy or resection, a sample of leftover tissue may be requested for analysis.

## **10.7 End of Study**

Once all data has been collected, analyzed, and completely evaluated on all subjects as defined in the statistical analysis plan and subjects have completed follow up, expired, withdrawn, or been lost to follow up, the study will be ended. The study may also be terminated early for any reason by the PI.

## **10.8 Early Withdrawal of Subject(s)**

### **10.8.1 Criteria for Early Withdrawal**

Subjects may voluntarily withdraw from the study at any time. The PI may also withdraw a subject from the study at any time based on his/her discretion. Reasons for PI-initiated withdrawal may include, but is not limited to the following:

- Adverse events
- Abnormal laboratory values
- Abnormal test procedure results
- Protocol deviation
- Administrative issues
- Disease progression
- Pregnancy

### **10.8.2 Follow-up Requirements for Early Withdrawal**

Patients in the treatment arm will be assessed and followed for adverse event monitoring/safety analysis for 30 days following Evolocumab injection.

### **10.8.3 Replacement of Early Withdrawal(s)**

Patients who are withdrawn by the PI prior to baseline PK collection (both arms) and Evolocumab injection (treatment arm) will be replaced. Patients who do not undergo surgery or biopsy or do not have sufficient tissue taken for the pharmacokinetic LC-MS analysis to assess for the presence of evolocumab (treatment arm) will be replaced. If there is no enough tissue available for analysis in either cohort, the patients should be replaced.

## **10.9 Study Assessments**

### **10.9.1 Medical History**

Medical history will be obtained from the Duke electronic system and from the subject and/or family at the screening visit and reviewed at each study visit. This data may include the following:

- All past medical and surgical history
- Current medications
- Changes in physical or neurologic symptoms
- Any adverse events

### **10.9.2 Physical Exam**

Vital signs and physical and neurologic examinations will be assessed for patients in the treatment arm and recorded prior to enrollment and at each visit according to Table 4.

### **10.9.3 Correlative Assessments**

The following will be tested from tumor and serum samples (both study arms):

1. Lipid metabolism and immune characteristics (multi-omics analysis, immune infiltration and T cell profiling) of tumor cells taken from resected or biopsied samples
2. Analysis of tumor cells expressing MHC-I will be performed by fluorescence-activated cell sorting (FACS)
3. Analysis of serum levels of evolocumab, for comparison to intratumoral concentrations
4. Differential levels of TILs based on flow cytometry after staining of cells for expression of surface and nuclear markers of exhaustion (e.g., PD-1, Lag3, TIM3) and activation (CD137)

## **11 SAFETY MONITORING AND REPORTING**

The PI is responsible for the identification and documentation of adverse events and serious adverse events, as defined below. Among patients receiving evolocumab and at each study visit, the PI or designee must assess, through non-suggestive inquiries of the subject or evaluation of study assessments, whether an AE or SAE has occurred.

### **11.1 Adverse Events**

An adverse event (AE) is any untoward medical occurrence in a patient receiving study drug in the treatment arm and which does not necessarily have a causal relationship with this treatment. For this protocol, the definition of AE also includes worsening of any pre-existing medical condition. An AE can therefore be any unfavorable and unintended or worsening sign (including an abnormal laboratory finding), symptom, or disease temporally associated with the use of Evolocumab, whether or not related to use of the Evolocumab. Abnormal laboratory findings without clinical significance (based on the PI's judgment) should not be recorded as AEs. But laboratory value changes that require therapy or adjustment in prior therapy are considered adverse events.

From the time a patient receives their Evolocumab injection to the End of Study visit (as defined in Section 10.7), all AEs must be recorded in the subject medical record and adverse events case report form.

AEs will be assessed according to the CTCAE version 5.0. If CTCAE grading does not exist for an AE, the severity of the AE will be graded as mild (1), moderate (2), severe (3), life-threatening (4), or fatal (5).

Attribution of AEs will be indicated as follows:

- Definite: The AE is clearly related to the study drug
- Probably: The AE is likely related to the study drug
- Possible: The AE may be related to the study drug
- Unlikely: The AE is doubtfully related to the study drug
- Unrelated: The AE is clearly NOT related to the study drug

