#### 7.1.2 Definition of Dose-Limiting Toxicity (DLT)

Among patients treated with Evolocumab, toxicities will be graded according to the National Cancer Institute (NCI) Common Terminology Criteria for Adverse Events (CTCAE) version 5 criteria. DLTs will be defined as any of the following events that are at least (possibly, probably, or definitely) attributable to study treatment (i.e., evolocumab):

- Any Grade 3 or any Grade 4 toxicity (at least possibly, probably, or definitely attributable to study treatment [i.e., evolocumab]) that is not reversible (i.e., reversible means the toxicity is trending towards improvement and has downgraded to at least Grade 2 or back to baseline) within 2 weeks, including cerebral edema or worsening neurologic symptoms

- Any life-threatening event (at least possibly, probably, or definitely attributable to study treatment [i.e., evolocumab]) that is not reversible (i.e., reversible means the toxicity is trending towards improvement and has downgraded at least to Grade 2 or back to baseline) within 2 weeks
- Treatment-related death at least possibly, probably, or definitely attributable to study treatment (i.e., evolocumab).
- Any grade 2 or higher serious autoimmune toxicities, particularly those affecting vital organs (e.g., cardiac, renal, CNS) occurring within 2 weeks of any protocol treatment (i.e., evolocumab).

Exceptions to the above DLT definition include:

- Seizures: Due to the nature of the disease under investigation in this protocol, patients may have pre-existing seizures or be susceptible to new seizures as a result of the underlying disease process. Although seizures may be defined as Grade 3 or 4 toxicities under NCI CTC, and will be reported as such in this protocol, seizures will not be considered an unacceptable adverse event if, in the opinion of the Principal Investigator they have not increased in frequency or can be attributed to another recognized cause of increasing seizure frequency such as sub-therapeutic anti-convulsant levels or biopsy proven tumor progression.

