### **11.1.2 Reporting of AEs**

A summary of all adverse events (not just those considered related to the study drugs) will be kept. AEs will be categorized by organ system, relationship to which treatment, grade of severity, and resolution. Weekly review by the PI during weekly Adverse Event meeting of new AEs and the collective AEs will occur with the intention of identifying any trends or patterns in toxicity. If significant toxicity is observed in the initial 2 patients, or after the first month, the study will be paused, and protocol modification will be considered. If any DLT occurs, as defined in Section 7.1.2, the study will be paused for assessment/review to determine if any changes to the protocol are warranted.

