## **12 QUALITY CONTROL AND QUALITY ASSURANCE**

### **12.1 Monitoring**

This clinical research study will be monitored both internally by the PI, and institutionally by the Duke Cancer Institute (DCI). In terms of internal review, the PI will continuously monitor and tabulate adverse events. Appropriate reporting to the Duke University Medical Center IRB will be made. If an unexpected frequency of Grade III or IV events occur, depending on their nature, action appropriate to the nature and frequency of these adverse events will be taken. This may require a protocol amendment, dose de-escalation, or potentially closure of the study. The PI of this study will also continuously monitor the conduct, data, and safety of this study to ensure that:

- Interim analyses occur as scheduled;
- Stopping rules for toxicity and/or response are met;
- Risk/benefit ratio is not altered to the detriment of the subjects;
- Appropriate internal monitoring of AEs and outcomes is done;
- Over-accrual does not occur;
- Under-accrual is addressed with appropriate amendments or actions;
- Data are being appropriately collected in a reasonably timely manner.

DCI Protocol Review and Monitoring systems (PRMS) review of this protocol begins with an initial review by the Cancer Protocol Committee (CPC). CPC new protocol review focuses on scientific relevance, study design, adequacy of biostatistical input, protocol prioritization, feasibility of completing the study within a reasonable time frame and risk assessment of the trial. The PI will abide by CPC assessment of the level of risk, which will determine the intensity of subsequent DCI monitoring. CPC also conducts annual scientific progress reviews on protocols that are open to enrollment and focus on protocol prioritization, accrual and scientific progress. These reviews are conducted at the time of IRB annual renewals and documentation of all CPC reviews will be maintained in eIRB/iRIS systems.

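### The laboratory filter in Section 11.1 has no grade limit, so an untreated Grade 3-4 change judged insignificant drops out of the AE record and may not reach DLT review

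*Combined protocol and SAP*

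**What the plan says.** Section 11.1 includes abnormal laboratory findings in its definition of an AE and then narrows it: "Abnormal laboratory findings without clinical significance (based on the PI's judgment) should not be recorded as AEs". The next sentence restores part of what was removed: "But laboratory value changes that require therapy or adjustment in prior therapy are considered adverse events". Neither sentence mentions grade. Grading comes afterwards and applies to AEs: "AEs will be assessed according to the CTCAE version 5.0". The attribution scale that follows is also defined for AEs.

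Section 7.1.2 states that "toxicities will be graded according to the National Cancer Institute (NCI) Common Terminology Criteria for Adverse Events (CTCAE) version 5 criteria". Its first DLT criterion starts from "Any Grade 3 or any Grade 4 toxicity" and adds two conditions: at least possible attribution to evolocumab, and no reversal within 2 weeks. Clinical significance is not among the conditions, and the listed exceptions contain no general one for laboratory values.

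Two sections act on these events. Section 11.1.2 says "If any DLT occurs, as defined in Section 7.1.2, the study will be paused for assessment/review", and Section 7.1.1 has a matching pause. Section 12.1 has the investigator tabulate AEs and opens its rule with "If an unexpected frequency of Grade III or IV events occur". What follows is discretionary, with no numeric threshold and no mandatory pause.

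**The concern.** Whether a laboratory value enters the AE record depends on a judgement of significance. Whether it matters for safety decisions depends largely on its grade. The two tests need not agree, and the significance test comes first. A high-grade value that needed no treatment can be left out by a stated rule of the protocol, without any oversight in conduct.

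The consequence is limited but concrete. The study treats at most 10 patients, and a single DLT pauses it, so one qualifying event that was not reviewed would matter. An unrecorded value also has no documented attribution, so a later reader could not see why it was set aside.

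**Working it through.** No arithmetic applies. The documents give no laboratory event rate, and the sample size in Section 13.8 rests on practical grounds. The check is to follow a post-dose laboratory change through the sections.

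**Step 1: does it enter the AE record (Section 11.1)?**

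| Post-dose laboratory change | Recorded as an AE? |
|---|---|
| Needs therapy or a change in therapy | Yes |
| Untreated, judged clinically significant | Yes |
| Untreated, judged not significant, Grade 1-2 | No |
| Untreated, judged not significant, Grade 3-4 | No |

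The last row is the gap. The third row does not touch the Grade 3-4 rules. Section 7.1.2 does have a separate criterion starting at Grade 2 for autoimmune toxicities, but it requires them to be serious, so a finding without clinical significance would hardly meet it.

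**Step 2: what happens to the last row in Section 12.1?** The loss is direct. The rule works from the investigator's tabulation of AEs, and an unrecorded value is not in it. The same holds for the AE summaries in Section 13.1. Section 13 plans no separate table of laboratory values or grade shifts, so the value appears in no planned safety output.

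**Step 3: what happens to it in Section 7.1.2?** It would be a DLT only if it were also at least possibly attributable and not reversed within 2 weeks. A value can meet those conditions while being untreated and judged insignificant, so the overlap is possible but small. Whether such a value reaches DLT review turns on the word 'toxicity', which the protocol does not define in relation to recorded AEs.

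- Pointing towards recorded AEs: the exceptions in Section 7.1.2 are worded in terms of adverse events; the attribution a DLT needs is defined only for AEs (Section 11.1); and the weekly review that looks for toxicity patterns, like one statement of the DLT pause, sits in the section on AE reporting (Section 11.1.2).
- Pointing the other way: Sections 7.1.1 and 7.1.2 speak of toxicity that is observed or graded, and neither makes an AE entry a precondition.

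**Step 4: is the order of operations consistent?** For seizures, thromboembolism and SIADH, among others, Section 7.1.2 has the event reported at its grade even where it is then not counted as unacceptable. Those events are recorded first and exempted second. Section 11.1 reverses that order for laboratory values.

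**Step 5: does another section close the gap?** None requires a Grade 3-4 laboratory value to be recorded whatever the investigator's judgement. Table 4 and Section 10.4 schedule one post-dose CBC and CMP, about 2 weeks after the procedure, so no later planned sample would bring the value to light.

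**The case against.** The strongest reply is that the DLT rule is not tied to AE entries. Section 7.1.1 pauses the trial on any evidence of a DLT, and Section 11 requires the investigator or designee to evaluate study assessments at each visit. A reader might infer from Section 11.1 that Grade 3-4 laboratory changes bypass DLT review and the pause. The documents do not support that as a stated consequence; it is one reading of an undefined term. This part of the reply stands.

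Three further points also stand. To be lost as a DLT, a value must be Grade 3-4, attributable, non-reversing, untreated and judged insignificant, which is a narrow combination. The Section 12.1 rule carries no mandatory pause, so only the DLT route bears on one. And the investigator's judgement is not the only check: the institutional monitoring team reviews the adequacy of AE reporting, the Safety Oversight Committee reviews safety data and toxicities, and laboratory results remain in the source records.

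It can also be said that the same unblinded investigator assigns attribution, so the fix does not remove judgement. That is true, but a recorded attribution can be reviewed and an absent entry cannot. None of these replies points to a sentence requiring the value to be recorded.

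**Conclusion.** The point holds in limited form. Section 11.1 conflicts with the grade-based rules for one subset: Grade 3-4 laboratory changes that are untreated and judged not clinically significant. For the AE summaries and the Section 12.1 tabulation, the omission follows from the text. For DLT review it is possible, and it depends on 'toxicity' meaning recorded AEs.

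The size cannot be estimated from the documents. A reader might assume a per-patient rate of Grade 3-4 laboratory changes and project it over 10 patients. The documents give no such rate, and the result would be the chance of any such change, not of a missed DLT, which needs the further conditions above. Nor do the documents show that the DLT count will be biased downward; they show only that it can be. The protocol does not itself present an absence of DLTs as an absence of Grade 3-4 laboratory toxicity.

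This is a cheap improvement.

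**What to change.** Reconcile Section 11.1 with Sections 7.1.2 and 12.1 by limiting the clinical-significance filter to Grade 1-2 laboratory values. Add one sentence: every post-dose laboratory value of CTCAE Grade 3 or higher that is worse in grade than at screening is recorded as an AE with attribution and checked against Section 7.1.2. State in Section 7.1.2 how 'toxicity' relates to recorded AEs. The DLT criteria themselves are left to the investigators.

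The change uses data already collected and adds no follow-up sampling. With one scheduled post-dose sample, scheduled tests alone cannot show whether a value reversed within 2 weeks; that is a separate matter which this change does not settle.

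The cost is the added text and a few more AE lines in about 10 treated patients. Some lines will reflect post-operative or disease-related changes unrelated to the drug, and the existing attribution field can mark them as such.

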### **11.1.1 AEs of Special Interest**

Special Interest Adverse Events that may occur during the injection procedure include:

- Allergic reaction
- Anaphylaxis
- Pre-syncope
- Syncope
- Vasovagal reaction

Special Interest Adverse Events that may occur after the procedure, but may still be related to injection include:

- Injection site complications

### **11.1.2 Reporting of AEs**

A summary of all adverse events (not just those considered related to the study drugs) will be kept. AEs will be categorized by organ system, relationship to which treatment, grade of severity, and resolution. Weekly review by the PI during weekly Adverse Event meeting of new AEs and the collective AEs will occur with the intention of identifying any trends or patterns in toxicity. If significant toxicity is observed in the initial 2 patients, or after the first month, the study will be paused, and protocol modification will be considered. If any DLT occurs, as defined in Section 7.1.2, the study will be paused for assessment/review to determine if any changes to the protocol are warranted.

## **11.2 Serious Adverse Events**

An AE is considered “serious” if in the opinion of the investigator it is one of the following outcomes:

- Fatal
- Life-threatening
- Constitutes a congenital anomaly or birth defect
- A medically significant condition (defined as an event that compromises subject safety or may require medical or surgical intervention to prevent one of the three outcomes above).
- Requires inpatient hospitalization or prolongation of existing hospitalization
- Results in persistent or significant incapacity or substantial disruption to conduct normal life functions.

### **11.2.1 Reporting of SAEs**

All SAEs should be reported immediately to the PI, [name] ([contact]) or his designee [contact]).

All adverse events that are considered serious, unanticipated, and related or possibly related to the research (as defined by 21CRF312.32[a]) will be reported to the IRB using the appropriate SAE reporting process.

### **11.3 Emergency Unblinding of Investigational Treatment**

Not applicable.

### **11.4 Other Reportable Information**

Not applicable.

### **11.5 Special Warnings and Precautions**

Not applicable.

### **11.6 Safety Oversight Committee (SOC)**

The Duke Cancer Institute SOC is responsible for annual data and safety monitoring of DUHS sponsor-investigator phase I and II, therapeutic interventional studies that do not have an independent Data Safety Monitoring Board (DSMB). The primary focus of the SOC is review of safety data, toxicities and new information that may affect subject safety or efficacy. Annual safety reviews includes but may not be limited to review of safety data, enrollment status, stopping rules if applicable, accrual, toxicities, reference literature, and interim analyses as provided by the sponsor-investigator. The SOC in concert with the DCI Monitoring Team (see Section 12.1 for Monitoring Team description) oversees the conduct of DUHS cancer-related, sponsor-investigator greater-than-minimal-risk intervention studies that do not have an external monitoring plan, ensuring subject safety and that the protocol is conducted, recorded and reported in accordance with the protocol, standing operating procedures (SOPs), Good Clinical Practice (GCP), and applicable regulatory requirements.

### **11.7 External Data and Safety Monitoring Board (DSMB)**

There is no external DSMB for this study.

## **12 QUALITY CONTROL AND QUALITY ASSURANCE**

### **12.1 Monitoring**

This clinical research study will be monitored both internally by the PI, and institutionally by the Duke Cancer Institute (DCI). In terms of internal review, the PI will continuously monitor and tabulate adverse events. Appropriate reporting to the Duke University Medical Center IRB will be made. If an unexpected frequency of Grade III or IV events occur, depending on their nature, action appropriate to the nature and frequency of these adverse events will be taken. This may require a protocol amendment, dose de-escalation, or potentially closure of the study. The PI of this study will also continuously monitor the conduct, data, and safety of this study to ensure that:

- Interim analyses occur as scheduled;
- Stopping rules for toxicity and/or response are met;
- Risk/benefit ratio is not altered to the detriment of the subjects;
- Appropriate internal monitoring of AEs and outcomes is done;
- Over-accrual does not occur;
- Under-accrual is addressed with appropriate amendments or actions;
- Data are being appropriately collected in a reasonably timely manner.

DCI Protocol Review and Monitoring systems (PRMS) review of this protocol begins with an initial review by the Cancer Protocol Committee (CPC). CPC new protocol review focuses on scientific relevance, study design, adequacy of biostatistical input, protocol prioritization, feasibility of completing the study within a reasonable time frame and risk assessment of the trial. The PI will abide by CPC assessment of the level of risk, which will determine the intensity of subsequent DCI monitoring. CPC also conducts annual scientific progress reviews on protocols that are open to enrollment and focus on protocol prioritization, accrual and scientific progress. These reviews are conducted at the time of IRB annual renewals and documentation of all CPC reviews will be maintained in eIRB/iRIS systems.

A determination for the degree of monitoring conducted by the DCI monitoring team is made at the time of initial CPC approval to commensurate with the type and level of intervention, phase, endpoints, degree of risk, size and complexity of the protocol. A formal, independent monitoring will be conducted by the DCI monitoring team according to the risk level and monitoring plan assigned by the CPC until the study is closed to enrollment or subjects are no longer receiving study drug or other interventions that are more than minimal risk. Additional monitoring may be prompted by findings from monitoring visits, unexpected frequency of serious and/or unexpected toxicities, or other concerns. Monitoring visits may also be initiated upon request by DUHS and DCI Leadership, CPC, SOC, a sponsor, an investigator, or the IRB.

The DCI monitoring team reviews the adequacy of informed consent, enrollment of eligible patients, implementation of protocol-specified procedures and treatment, adequacy of data collection, and appropriateness of adverse event monitoring and reporting. The DCI monitoring team presents final monitoring reports to the DCI Safety Oversight Committee (SOC) highlighting safety concerns and unresolved issues. The SOC, at a convened meeting, assigns an overall rating of satisfactory, marginal, or unsatisfactory to reflect the overall quality of data, regulatory, consent, eligibility, study conduct and AE reporting. Corrective action plans (CAPs) are developed, implemented, and evaluated as indicated. The SOC will notify the sponsor-investigator and DUHS IRB when significant safety concerns are identified.

The SOC in concert with DCI monitoring team conducts data and safety monitoring for DUHS sponsor-investigator phase I and II, therapeutic interventional oncology studies that do not have an independent DSMB. These reviews occur at a minimum annually and more frequently for the high risk studies. The SOC safety reviews include review of safety data, enrollment status, stopping rules if applicable, accrual, toxicities, reference literature, and interim analyses as provided by the sponsor-investigator. The SOC, at a convened meeting, assigns a rating of satisfactory when adequate accrual with lack of excessive toxicity is present.

